1. INTRODUCTION

The pivotal Phase 3 POLAR program, studying calmagafodipir for the prevention of chemotherapy induced peripheral neuropathy, consists of two studies: POLAR-A and POLAR-M.

- POLAR-A is a placebo controlled, randomised (1:1) Phase III study of calmagafodipir 5 µmol/kg in combination with mFOLFOX6 compared to placebo+mFOLFOX6 in patients with adjuvant treatment of stage III or high-risk stage II colorectal cancer.
- POLAR-M is a placebo controlled, randomised (1:1:1) Phase III study of calmagafodipir in two different doses, 2 µmol/kg and 5 µmol/kg in combination with mFOLFOX6 compared to placebo+mFOLFOX6 in patients with metastatic CRC.

Patient recruitment in the POLAR-A and POLAR-M studies was initiated in late 2018 with the first patient randomised in on January 15, 2019, in POLAR-A and on POLAR-M on January 21, 2019.

On January 23, 2020, the Sponsor announced that the US Food and Drug Administration (FDA) had issued a clinical hold in the US of the POLAR program. The implication was that recruitment and dosing of patients in the POLAR-M study was halted in the US. Based on the evaluation of the independent Drug Safety Monitoring Board (DSMB), the Sponsor's position was that the overall safety profile for PledOx supported the continuation of the POLAR program and both studies continued as planned in Europe and Asia with dosing and further recruitment.

On March 1, 2020, the Sponsor decided to place recruitment and dosing of patients in the POLAR program on hold. The decision followed interactions with the French regulatory authority, ANSM, and the clinical hold issued by the US Food and Drug Administration (FDA) earlier in the year and was due to 4 observed events related to seizure. The Sponsor maintained its position that these events are not related to calmagafodipir, a position which was also supported by the DSMB and an additional independent external evaluation of these cases.

On April 6, 2020, the Sponsor decided to close the POLAR program early with a data cut-off targeted for the third quarter 2020 (further detailed later in this document). The decision was taken after a recommendation from the DSMB to stop the studies due to an accumulation of severe allergic reactions, primarily observed after repeated dosing.

Based on the development of the POLAR studies, a re-assessment of the sample size assumptions is needed to determine a reasonable statistical approach to the analysis of the POLAR studies.

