The POLAR studies were designed based on the following sample size assumptions:

- POLAR-A: With 112 patients per group, the POLAR-A study has 91% power to detect a reduction (improvement) from 40% to 20% (OR = 0.375) in the primary endpoint using two-sided test controlled at the 0.05 type-I error rate. To account for 20% dropout in the study, in total 280 patients (140 patients per arm) will be randomised.
- POLAR-M: With 112 patients per group, the POLAR-M study has 91% power to detect a reduction (improvement) from 40% to 20% (odds ratio = 0.375) in the primary endpoint using two-sided test controlled at the 0.05 type-I error rate. To account for 20% dropout in the study, in total 420 patients (140 patients per arm) will be randomised.

Table 1: Patient disposition in the POLAR studies

	POLAR-A	POLAR-M	Total
Number of patients randomised	301	290	591
Number of patients dosed with ≥ 1 cycle of IMP	297	285	582
Number of patients dosed with ≥ 6 cycles of IMP	257	194	451
Number of patients dosed with ≥ 12 cycles of IMP	107	98	205

A total of 591 patients was randomised in the POLAR program and 582 patients dosed, of which 451 patients completed 6 cycles and 205 patients completed 12 cycles (see Table 1).

There are two main contributing factors to take into account when designing a reasonable statistical approach to the analysis of the POLAR studies:

- 1) POLAR-M only randomised 290 out of the planned 420 patients. This, together with the reduced dosing of patients (see bullet 2 below) means a separate primary analysis based on this data set cannot be supported.
- 2) Due to the Sponsor's decision to place the dosing of patients on hold on March 1, 2020, not all patients have had sufficient dosing of IMP to expect the full treatment effect of active treatment as assumed in the sample size calculation.

Taking these two aspects into consideration account (the fewer number of randomised patients and the reduced dosing of patients) a reasonable statistical approach is to conduct a combined primary analysis across the two studies, with the data from the two studies regarded as strata, based on a modified ITT analysis set defined by the eligibility of dosing with IMP as intended in the clinical study protocol. In addition, a standalone analysis of the primary endpoint in the fully recruited POLAR-A study will be conducted if the combined analysis is statistically significant. This approach will be further detailed in this document.

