2.5 Changes From the Protocol Planned Analysis

Premature stop of administration of IMP in both POLAR-A and POLAR-M as well as the premature stop of recruitment in POLAR-M has several implications for the statistical analyses and the evaluation of the study data:

- Primary analysis. The Cochran-Mantel-Haenszel method described in the protocols has been fully specified to also include adjustment for cumulative oxaliplatin exposure. This amounts to replacing N, the number of subjects, in the divisor of the event rate calculation with cumulative oxaliplatin exposure. Also, in the protocols the CMH approach also adjust for FACT/GOG at baseline, but since there were very few patients with CIPN at baseline the primary analysis described in Section 5.1.1. does not include FACT/GOG at baseline.
- A negative binomial model will also be applied to the primary endpoint data as a supportive or exploratory analysis.
- Earlier stop of recruitment in POLAR-M has resulted in actual n=290 randomised patients as compared to the planned n=420.
- The primary analysis will be on the combined dataset including both POLAR-A and POLAR-M where study will be used as a stratification factor in all statistical analyses. Both studies will also be reported separately (see details in Section 3).
- Due to the lack of exposure of IMP a modified ITT (mITT) analysis set has been defined that will replace the Full Analysis Set (FAS). See further details in Section 3.1.
- Statistical analyses and summary tables will include data up to 12 months after the first dose of IMP (Assessment Visit 4). Data that has been collected after Assessment Visit 4 will only be included in the listings by patient.

Miscellaneous changes from the protocol planned analyses:

- The endpoint “mean health index using the FACT/GOG” as stated in the protocols will not be analysed.
- The variable Body Temperature although specified in vital signs section of the protocol has not been collected in the studies.
- In the CSP it says “PledOx Toxicities” but has been re-defined here in the SAP as “IMP Toxicities” since that is the way the data is collected and reported.

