3.1 Analysis Sets

The analysis set “All randomised patients (ITT)” consists of all patients who were assigned a randomisation number, irrespective of the treatment they received, if any.

The modified ITT (mITT) analysis set includes patients that fulfil at least one of the following criteria:

1. the patient was randomised prior to December 1, 2019 (ie the patient was eligible for at least 3 months of IMP) and had at least one post-baseline assessment for efficacy, or
2. the 3 month Assessment Visit occurred prior to 1 March, 2020, or
3. the patient received the 6th cycle of IMP after 1 March, 2020.

Patients will be analysed according to the treatment they are assigned to at randomisation, irrespective of what treatment they actually received.

The safety analysis set (SAF) consists of all randomised patients who receive at least one dose of IMP. Patients will be analysed according to the randomised study treatment actually received.

The list of patients to be included in each of the analysis sets is to be agreed between the project statistician and the Sponsor prior to unblinding, once all study data is available.

All enrolled patients will be listed indicating their membership to each analysis set along with the reason for exclusion.

The PK population (POLAR-M only) includes a subset of patients at pre-selected sites in all participating regions, where blood samples will be collected for pharmacokinetics and ECG assessments.

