6.1 Adverse Events

Adverse events will be recorded in the eCRF and will be coded according to the MedDRA dictionary Version 23.0. All AEs including SAEs will be collected up to 30 days after the last administration of IMP (or as of March 2nd., 2020, up to 30 days after the EOT) and followed until resolution.

A treatment-emergent adverse event (TEAE) is defined as an adverse event that started or worsened after the start of the administration of IMP. Treatment-emergent AEs will include AEs that occur after the first dose of IMP (i.e. day 1, Cycle 1) and end at the EOT visit (i.e. 14 days after the last dose of IMP). AEs will also be considered treatment-emergent if they are ongoing at first IMP infusion or start ≤ 30 days after the last dose of IMP. Adverse events with unknown start date/time will be assumed to be treatment-emergent unless the end date/time is known to be before administration of the first dose of IMP. Non-treatment emergent AEs will include any AEs that occur between informed consent and the first dose of IMP.

Allocation of AEs to study periods

All AEs and SAEs will be allocated to a study period depending on the onset date in relation to the date of administration of IMP:

Period 1: Time of informed consent until time before first dose of IMP (non-TEAE)

Period 2: Time of first dose of IMP until time of last dose of IMP + 30 days (TEAE)

Period 3: Time of last dose of IMP + 31 days and onwards (non-TEAE)

In case of complete or partial missing start or end date of an AE see details in Section 3.3.

Causality to the Investigational Medical Product (IMP)

- Not related
- Unlikely related
- Possibly related
- Probably related
- Definitely related

An AE/SAE is defined as related to IMP if the event is classified as Possibly, Probably or Definitely related.

Intensity of Adverse Events

- Mild
- Moderate
- Severe
- Life-threatening
- Death related to AE

No summaries will be done of AE/SAE by intensity but will be included in the listings.

Data presentations

If a patient experienced more than one TEAE the patient will be counted once for each SOC and once for each PT. System organ class and preferred terms will be ordered alphabetically first by SOC and then all PTs alphabetically within a SOC. Non-TEAEs will not be presented in summary tables, only in listings.

Tables: treatment-emergent AEs

- Number and percentage of patients experiencing TEAEs by SOC and PT for each treatment group and total

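### mITT criterion 3 counts a 6th IMP cycle only if given after 1 March 2020, the date of the decision to hold dosing, so patients with six cycles just before the hold can meet no criterion

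*SAP*

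**What the plan says.** Section 3.1 puts a patient in the mITT set if at least one of three criteria is met:

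1. randomisation before 1 December 2019, glossed as eligibility for at least 3 months of IMP, plus at least one post-baseline efficacy assessment;
2. "the 3 month Assessment Visit occurred prior to 1 March, 2020";
3. "the patient received the 6th cycle of IMP after 1 March, 2020".

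Section 1 gives the background: "On March 1, 2020, the Sponsor decided to place recruitment and dosing of patients in the POLAR program on hold". It repeats the date when explaining why the planned analysis had to change, citing the "decision to place the dosing of patients on hold on March 1, 2020", and describes the new set as a "modified ITT analysis set defined by the eligibility of dosing with IMP as intended in the clinical study protocol".

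Section 2.5 gives lack of IMP exposure as the reason for the set and says that "a modified ITT (mITT) analysis set has been defined that will replace the Full Analysis Set (FAS"). Section 5 makes mITT the default for all efficacy variables. Section 3.1 also defines an ITT set of all randomised patients, but no efficacy analysis is assigned to it.

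No section states the date of the last IMP dose. The nearest indication is in section 6.1, where the adverse event window changes "as of March 2nd., 2020, up to 30 days after the EOT". That fits a stop on 1 March but does not establish one.

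**The concern.** Criterion 3 treats a 6th cycle as sufficient for entry, but only when it falls after the date given for the decision to hold dosing. There is no counterpart for a 6th cycle on or before that date. A patient randomised from 1 December 2019 who had six cycles in time, but whose 3-month visit fell on or after 1 March, has no route into the set. A patient who had fewer cycles by the hold and one dose just after it does.

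This rule decides membership of the set used for the primary analysis. The patient list is to be agreed before unblinding, but the SAP does not say how the date in criterion 3 is to be applied, and no planned efficacy analysis would show whether the choice matters.

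**Working it through.** **Inputs from the SAP.** The three criteria (section 3.1). Hold decision on 1 March 2020 (section 1). Assessment visits counted from first dose, since section 2.5 refers to "data up to 12 months after the first dose of IMP (Assessment Visit 4"). US POLAR-M dosing halted with the hold announced on 23 January 2020 (section 1).

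**Assumptions.** The SAP does not state a cycle length. The base case is 14 days. Section 6.1 places the end-of-treatment visit 14 days after the last dose, and 12 cycles in 6 months gives 182.6 / 12 = 15.2 days. The base case also takes first dose on the day of randomisation, no delays, and the 3-month visit at 3 calendar months.

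**The SAP's own figure.** From 1 December 2019 to 1 March 2020 is 31 + 31 + 29 = 91 days, or 3 calendar months. Measured against 1 March, the 3-month gloss in criterion 1 reproduces.

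**Formulas.** Cycle 6 = first dose + 5 × cycle length, which is + 70 days at 14-day cycles. 3-month visit = first dose + 3 calendar months.

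| First dose | Cycle 6 | 3-month visit | Criteria met |
|---|---|---|---|
| 1 Dec 2019 | 9 Feb 2020 | 1 Mar 2020 | none |
| 5 Dec 2019 | 13 Feb 2020 | 5 Mar 2020 | none |
| 21 Dec 2019 | 29 Feb 2020 | 21 Mar 2020 | none |
| 22 Dec 2019 | 1 Mar 2020 | 22 Mar 2020 | none (1 March is not after 1 March) |
| 23 Dec 2019 | 2 Mar 2020 | 23 Mar 2020 | 3, if that dose was given |

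Starts from 1 to 21 December have six cycles by 29 February and meet no criterion: 21 days. The 23 December start has five cycles by 29 February and qualifies if dosed on 2 March.

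**Sensitivity.** Width of the gap in randomisation days, for lags from randomisation to first dose of 0 / 3 / 7 days:

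| Average cycle | Visit on time | Visit 7 days early | Visit 14 days early |
|---|---|---|---|
| 14 days | 21 / 18 / 14 | 14 / 14 / 14 | 7 / 7 / 7 |
| 15.2 days | 15 / 12 / 8 | 8 / 8 / 8 | 1 / 1 / 1 |
| 16 days | 11 / 8 / 4 | 4 / 4 / 4 | 0 / 0 / 0 |
| 18 days | 1 / 0 / 0 | 0 / 0 / 0 | 0 / 0 / 0 |

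With an on-time visit and no lag, the gap closes when 5 × cycle length reaches 91 days, at 18.2 days per cycle. The range is 0 to 21 days.

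**Who cannot be in the gap.** A US POLAR-M patient starting on 1 December would reach cycle 6 on 9 February at the earliest, after US dosing was halted. The POLAR-M 2 µmol/kg arm is outside the primary comparison (sections 3 and 5.1.1).

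**Number of patients.** Section 1 counts 451 patients with at least 6 cycles, but gives neither accrual nor 6th-cycle dates, so the number affected cannot be computed.

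**The case against.** The strongest reply is that section 1 speaks of eligibility for dosing, not of doses received. Criterion 1 makes that concrete as 3 months of opportunity before the hold. A patient starting on 21 December had only 70 days to 29 February, so leaving that patient out agrees with criterion 1. Section 2.5 explains why a new set was needed but sets no six-cycle threshold. This stands as far as it goes: a reader might infer a direct contradiction with section 1, and the text does not support that. The inconsistency lies inside section 3.1, where criterion 3 accepts a 6th cycle as an alternative to 3 months of opportunity but only on one side of the hold date. With section 1 and section 2.5 the tension is one of purpose.

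A second reply is that 1 March is the date of a decision, not of the last infusion, and criterion 3 may be meant for patients dosed around the stop. That also stands. A reader might infer that criterion 3 is necessarily empty, or that before was meant instead of after. Without a last-dose date the SAP supports neither inference.

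Third, the gap depends on assumed cycle length, lag and visit timing. Section 4.4.2 plans tables of oxaliplatin dose delays, so delays are expected, and the gap can vanish. This limits the size of the gap but does not touch the wording of criterion 3.

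Finally, the patient list is agreed before unblinding and the SAP is reviewed at the blind data review. These steps limit outcome-driven selection. They do not say which reading governs the list.

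**Conclusion.** The point holds. Criterion 3 counts a 6th cycle as sufficient only after the date given for the hold decision, the SAP gives no date on which dosing stopped, and earlier 6th cycles have no matching criterion. That much needs no assumption about cycles or visits. Followed literally, the rule can leave out patients with six cycles before the hold and admit patients with five, which sits poorly with the exposure rationale for the set.

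The gap is 21 days of randomisation dates in the base case and 0 to 21 days across the cycle lengths, lags and visit timings tested. It concerns non-US patients randomised in about the first three weeks of December 2019. It would be too strong to say that membership of everyone randomised from December depends on the reading. At 14-day cycles, accepting a 6th cycle on or before 1 March would add only starts up to 22 December.

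Nor does the SAP support a claim of bias between arms. The calendar cut-offs are the same in every arm, and the SAP gives no figures from which a difference could be derived.

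**What to change.** Before unblinding, reconcile criterion 3 in section 3.1 with section 1. State the date on which IMP dosing stopped, and correct or justify the restriction to after 1 March, so that patients with a 6th cycle before, on and after that date are handled consistently. If a 6th cycle on or before 1 March also counted, the base-case gap would close. This is a wording change. It may alter membership for some patients randomised in December 2019, by a number the SAP does not allow one to state.

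Also repeat the primary analysis on the ITT set already defined in section 3.1, as a sensitivity analysis, to show whether the result depends on mITT membership. It does not repair the wording. It costs one extra analysis, and it includes patients with little IMP exposure, so it should be read with that in mind.

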3.2 Hypothesis to be Tested

With respect to the primary endpoint Moderate to Severe CIPN at 9 months after first dose of IMP the statistical hypothesis to test is:

$$H_0: \mu_{5\mu\text{mol/kg}} = \mu_{\text{placebo}}$$

$$H_1: \mu_{5\mu\text{mol/kg}} \neq \mu_{\text{placebo}}$$

where μ_x represents the oxaliplatin-dose adjusted Moderate to Severe CIPN event rate at 9 months on treatment x . The treatment effect will be captured as the ratio of event rates, $\Psi = \mu_{5\mu\text{mol/kg}} / \mu_{\text{placebo}}$, so that the preceding null and alternative hypotheses can be reframed as

$$H_0: \Psi = 1 \text{ versus } H_1: \Psi \neq 1$$

A rate ratio <1 favours the PledOx 5µmol/kg group over placebo.

3.3 Handling of Dropouts or Missing Data

All reasonable efforts will be made to obtain complete data for all patients. However, missing observations may occur due to patients being lost to follow-up or non-compliant with the required protocol assessments.

Baseline

In all situations where baseline values are not recorded or not taken at the baseline visit (in most cases Cycle 1, Day 1), the value recorded from the last visit prior to Cycle 1 Visit will be used as the baseline value.

Handling of Incomplete Dates

Incomplete (partial or missing) dates will be presented in data listings as provided on the eCRF. However, for use in calculations (e.g. to calculate the duration of an AE or medication use) dates will be estimated as follows.

For partial start-dates:

- If the year is unknown, then the date will not be imputed and will be assigned a missing value.
- If the month is unknown, then:
 - i) If the year matches the year of the first dose date, then impute the month and day of the first dose date.
 - ii) Otherwise, assign 'January'.
- If the day is unknown, then:
 - i) If the month and year match the month and year of the first dose date, then impute the day of the first dose date.
 - ii) Otherwise, assign '01'.

For partial end-dates:

- If the year is unknown, then the date will not be imputed and will be assigned a missing value.
- If the month is unknown, then assign 'December'.
- If the day is unknown, then assign the last day of the month

If the above rules for end-dates result in an illogical date with regards to the dates the patient was in the study, then the end date will be replaced with the patient's date of completion/withdrawal. Furthermore, should the above rules not result in the most conservative date (as described below), then the imputed value may be replaced by a date that will lead to a more conservative analysis.

After implementing the rules above, to determine whether AEs with incomplete start or stop dates are non-treatment-emergent or treatment-emergent the following strategy will be used:

- If the start date and stop date are both missing, the most conservative approach is taken and the AE is considered to be treatment-emergent.
- If the start date is missing but the stop date is not missing and is on or after the day of first study drug administration then the most conservative approach is taken and the AE is considered to be treatment-emergent.
- If the start date is missing but the stop date is not missing and is before the day of first study drug administration then the AE is considered to be non-treatment-emergent.

If the date of first and/or last dose of study drug administration is missing then duration of exposure will be set to missing.

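### The partial start-date rule in SAP Section 3.3 ignores the stop date, so an AE that ended before first dose can be given an onset after its resolution and, on the literal order of steps, be counted as treatment-emergent

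*SAP*

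**What the plan says.** Section 3.3 (Handling of Incomplete Dates) gives these rules for partial start dates:

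- Day unknown: "If the month and year match the month and year of the first dose date, then impute the day of the first dose date".
- Month unknown: "If the year matches the year of the first dose date, then impute the month and day of the first dose date".
- Year unknown: "If the year is unknown, then the date will not be imputed and will be assigned a missing value".

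For end dates only, there is a repair clause that begins "If the above rules for end-dates result in an illogical date". It tests the date against the patient's time in the study.

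The section then says that treatment-emergence is decided once these rules have been applied. One branch of that strategy begins "If the start date is missing but the stop date is not missing and is before the day of first study drug administration" and makes the AE non-treatment-emergent.

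Section 6.1 (Adverse Events) allocates AEs to periods by onset date. Period 2, from first dose to 30 days after last dose, is treatment-emergent. The section classes AEs between informed consent and first dose as non-treatment-emergent. It treats an AE with unknown start as treatment-emergent "unless the end date/time is known to be before administration of the first dose of IMP". For completely or partially missing dates it refers back to Section 3.3.

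**The concern.** A stop date before first dose shows that the event ended before treatment. The start-date rules do not use that information. They can therefore create a record that resolves before it begins, with its onset moved onto the day of first dose.

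The classification decides whether an event is tabulated at all, because Section 6.1 puts non-TEAEs in listings only. A pre-dose event moved into Period 2 could therefore enter a summary table where it does not belong. The AE listing, which reports onset and resolution relative to first dose, would show an order of dates that cannot be true.

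**Working it through.** There is no sample-size or power figure to reproduce. The check applies the Section 3.3 rules, and then the Section 6.1 period allocation, to example dates. The dates are assumed for illustration: first dose 20 Jun 2019 and last dose 20 Nov 2019. Duration is stop − start + 1.

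| Recorded start | Known stop | Imputed onset (3.3) | Duration | Does the 3.3 stop-date exception apply, read literally? | Status |
|---|---|---|---|---|---|
| June 2019, day unknown | 15 Jun 2019 | 20 Jun 2019 | −5 + 1 = −4 days | No, the start has been filled | Period 2, TEAE |
| 2019, month unknown | 10 Mar 2019 | 20 Jun 2019 | −102 + 1 = −101 days | No, the start has been filled | Period 2, TEAE |
| Year unknown | 15 Jun 2019 | stays missing | not defined | Yes | non-TEAE |

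The first and third rows share the same stop date. The event with the better-recorded start is classed as treatment-emergent, and the event with no usable start is classed correctly.

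The day-unknown case has no exceptions. Take every 2019 first-dose date with every earlier stop day in the same month. Each 31-day month gives 0 + 1 + … + 30 = 465 pairs, each 30-day month 435, and February 378. The total is 7 × 465 + 4 × 435 + 378 = 5373. All 5373 pairs give an onset after the stop and, on the literal order, TEAE status. This confirms the logic; it says nothing about how often such records occur.

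The clauses that might catch the problem do not:

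- The illogical-date repair is limited to end dates and does not compare start with stop.
- Replacement by a more conservative date is optional, and Section 3.3 uses 'conservative' to mean treatment-emergent, so it does not lead to a correction here.
- The stop-before-first-dose exception refers to a missing start and is applied after imputation. By then only a start with unknown year is still missing.
- The Section 6.1 clause that includes AEs ongoing at first infusion does not cover an AE that has already stopped.

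**The case against.** The strongest reply is that 'missing' in the exception was meant to include partial dates. The text gives this real support. Section 3.3 introduces incomplete dates with "Incomplete (partial or missing) dates will be presented in data listings as provided on the eCRF", so incomplete covers both kinds, and the treatment-emergence strategy is introduced as covering incomplete dates. Section 6.1 speaks of dates that are completely or partially missing and, directly after defining the periods, defers to Section 3.3. On that reading the exception governs, and the example AE is non-treatment-emergent. This stands: the misclassification depends on how 'missing' is read.

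A reader might also infer that Section 3.3 flatly contradicts the Section 6.1 sentence on unknown start dates. That requires reading 'missing' narrowly in one section and 'unknown' broadly in the other. Read both narrowly and that sentence does not cover partial dates; read both broadly and the two sections agree. The conflict on the literal order is with the Section 6.1 definition of non-TEAEs as events between consent and first dose.

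The reply does not remove the impossible onset date. The start-date rule produces it under either reading, and no clause limits an imputed start to the stop date.

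**Conclusion.** The point holds as a defect in a stated rule. The onset after resolution follows under any reading. The false TEAE status follows on the literal order of steps and is avoided on the broader reading of 'missing'.

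The size is limited, and several larger inferences are not supported:

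- **Not every such AE adds to a table.** Section 6.1 counts a patient once per SOC and once per PT, so a count rises only where the patient has no genuine TEAE in that SOC or PT.
- **No special bearing on infusion reactions on the first dosing day.** Section 1 says the severe allergic reactions were seen mainly after repeated dosing, and no AE table is organised by day of onset.
- **No identified effect on duration or medication results.** Section 3.3 gives its purpose as "for use in calculations (e.g. to calculate the duration of an AE or medication use) dates will be estimated as follows", but Section 6.1 plans no AE-duration summary and Section 4.3.3 plans only counts and percentages of medications.
- **No known frequency.** The fault needs a partial start matching the first-dose month or year together with a known earlier stop. The SAP gives no count, so the pattern cannot be called typical.
- **No evidence of bias between arms.** The rule does not refer to treatment.

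What is exposed is TEAE patient counts, to an unknown and probably small extent, and derived onset times in the AE listing. Efficacy endpoints are unaffected. The correction is still worth making, because programmers following the text could reach different classifications for the same event.

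**What to change.** In Section 3.3:

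1. Impute the first-dose date only if the stop date is missing or falls on or after first dose. Otherwise use the earliest date the known parts allow, never later than the stop date.
2. Extend the stop-before-first-dose exception to missing or partial start dates, so that these AEs are non-treatment-emergent. Status then does not depend on the imputed onset.

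On the example dates:

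- Start June 2019, stop 15 Jun: onset 1 Jun, duration 15 days, non-TEAE.
- Start 2019, stop 10 Mar: onset 1 Jan, duration 31 + 28 + 10 = 69 days, non-TEAE.
- Start June 2019, stop 25 Jun: onset stays at 20 Jun, duration 6 days, TEAE as now.

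The cost is one added condition, one changed word in the exception, and the matching edit to the date program. Made before the SAP is finalised and the blind is broken, it leaves unchanged every event whose stop date is missing or on or after first dose.
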